2.4. Statistical Testing Framework

All statistical tests will be conducted as two-sided tests of inequality. For example, as our primary analysis, we will test the hypothesis that the ratio of the intervention:control proportions, a relative risk (RR) measure, is significantly smaller than 1 with a two-sided test: **RR \neq 1 vs RR = 1**.

2.5. Timing of Final Analysis

The final analysis will take place after all chart reviews have been completed for the 24-month time point. This will occur after the three-month window closes for the youngest participant's second birthday.

2.6. Timing of Outcome Assessments

Endpoints are assessed briefly at 3-month intervals and in depth at 12 and 24 months of age. These include diagnosed AD, severity of symptoms, and development of potentially related conditions, such as allergies.

Table 2. Timing of assessments

Assessment	Child age	Window
Screening	≤ 2 months	0-9 weeks
Contact 1	≤ 2 months	0-9 weeks
Contact 2	3 months	± 14 days
Contact 3	6 months	± 14 days
Contact 4	9 months	± 14 days
Contact 5	12 months	-4 weeks + 12 weeks
Contact 6	15 months	± 14 days
Contact 7	18 months	± 14 days
Contact 8	21 months	± 14 days
Contact 9	24 months	-4 weeks + 12 weeks
Final Contact	24 months chart audit	Through 27 months of age

2.7. Study Schema

Parentheses (•) indicate that a measure applies to a subset of participants, e.g. intervention arm only, or only children with diagnosed AD.

Table 3. Study schema

Schedule of events		Screening	Contact 1	Contact 2	Contact 3	Contact 4	Contact 5	Contact 6	Contact 7	Contact 8	Contact 9
Child age (months)		≤ 2	≤ 2	3	6	9	12	15	18	21	24
Procedures											
Consent		•	•								
Assessment of Eligibility (Inclusion/Exclusion criteria)		•									
Baseline	Demographics		•								
	AD Risk		•								
	Living Environment		•								
	Pet Ownership		•								
	Alternate Contact		•								
Provide/Update Contact Info			•	•	•	•	•	•	•	•	
Quarterly Contact	Confirm PCP		•	•	•	•	•	•	•	•	•
	AD diagnosis		•	•	•	•	•	•	•	•	•
	Study arm adherence		•	•	•	•	•	•	•	•	•
Choose and ship emollient (Intervention Group Only)		(•)		(•)		(•)		(•)			
Assessment of AE/SAE			•	•	•	•	•	•	•	•	•
Annual Questionnaire	mAPI and ISAAC					•					•
	CEQ					•					•
	UK Working Party					•					•
	Sleep loss					•					•
	Allergies					•					•
Study arm adherence						•					•

Chart Abstraction	Medication history						•				•
	PGH-7 Global Health						•				•
	Infant diet						•				•
	Emollient acceptability (Intervention Group Only)						(•)				(•)
	If infant develops AD: -AD age of onset -Global severity of AD -IDQOL -POEM						(•)				(•)
	AD or eczema diagnosis by HCP						•				•
	Intensity of AD						(•)				(•)
	Medication history						(•)				(•)
	Other allergy diagnoses						(•)				(•)
	Assessment of AE/SAE						•				•

3. Statistical Principles

3.1. Level of Statistical Significance

In the primary analysis, use a type I error rate of 0.05. Secondary outcomes will be considered significant at $\alpha=0.05$ and exploratory analyses at $\alpha=0.1$. All tests will be two-tailed.

3.2. Adjustment for Multiplicity

To address type 1 error, we have specified a single primary outcome and provided detailed plans for secondary and exploratory analyses, many of which have correlated outcomes because they address alternative definitions of the same endpoint, or because they arise from a common cause. We plan to make all findings available with sufficient detail for readers to perform adjustments to a different false discovery rate if needed.

3.3. Confidence Intervals

Estimates will be reported with 95% confidence intervals.

3.4. Adherence

Participants in the intervention arm receive instructions to apply emollient daily, while those in the control arm are asked to refrain from emollient use. Frequency of emollient use, measured in days per week, is assessed for participants in both arms at each of the quarterly contacts from when the child is 3 months old to 24 months old. Participants are reminded of instructions per treatment arm at each quarterly and annual contact. Frequency of emollient use will be analysed as described in section 5 below.

3.5. Protocol Deviations

A deviation is any departure from the defined procedures as outlined in the study protocol that is not prospectively approved by the IRB. Deviations are unplanned and/or unintentional events.

Deviations will be assessed by the PI, then reported to the IRB, DSMB and the NIAMS.

Descriptions of all protocol deviations are included in bi-annual DSMB meetings, and are presented in both the open and closed reports.

3.6. Analysis Populations

The **Intention-to-Treat (ITT) Population** will contain all randomized participants. Missing outcomes will be multiply imputed to reduce bias without exaggerating precision per recommendations by Little and Yau for longitudinal studies³.

The **Complete Case Population** will include the subset of participants with non-missing primary outcomes.

The **Per-Protocol Population** will assign participants who report emollient use to the intervention arm (regardless of randomization), and those who report no emollient use to the control arm. This dataset will be used to estimate the relationship between frequency of emollient use and AD.

The **Safety Population** includes all randomized participants. Safety outcomes are reviewed regularly by the DSMB.

The **AD Population** includes children with diagnosed AD (chart review).

4. Trial Population

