3.3 Treatment Arms

There are two arms in the study- intervention and control. Both study arms will receive text messages and e-mail links providing general skin care educational material

throughout the study. This general skin care information includes information regarding the use of gentle cleansers, bathing safety tips and managing rash. All dyads will be reminded of their treatment arm every three months via electronic survey and e-mail. Both arms will be contacted at the same frequency. There are no evidence-based guidelines for frequency of bathing. Because bathing practices vary between families considerably, only general bathing tips will be provided to both groups.

3.3.1 *Intervention Arm*

Dyads assigned to the intervention arm will receive a study-approved emollient of their choice by mail at regular intervals throughout the study and instructed to use the emollient once-daily over the entire body. Parents may avoid the scalp, if needed. Quarterly reminders will be sent during the course of the study instructing parents on the daily use of the study emollient. In addition, the intervention group will receive general infant skin care information identical to the control group.

3.3.2 *Control Arm*

Dyads assigned to the control arm will be instructed to refrain from routine emollient use and only use emollients on an “as needed” basis if their baby develops dry skin. Like the intervention group, dyads in the control arm will also receive general infant skin care guidelines. Information in the control educational materials will include general infant skin care recommendations, such as bathing and rashes. The information in educational materials will be current standard of care for the topics included.

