10.4.3 Secondary analyses of primary endpoint

As a sensitivity analysis, we will perform a complete-case analysis using only subjects who have non-missing outcome data in a logistic regression model adjusting for stratification variables as well as covariates that we find to be associated with missing AD status.⁷⁸ The effect of emollient use will be evaluated with a model similar to the primary analysis, but substituting an indicator of regular reported emollient use (≥ 3 days per week) for intervention allocation. In a separate model, we will include a variable for bathing frequency. In the likely case that bathing and emollient use frequency are associated, we will create and test a combined categorical variable. We will return to the primary intervention-effect model and consider additional covariates previously found or suspected to be associated with AD, such as climate, season of birth, pet ownership, bathing frequency, and characteristics of the living environment using a change-in-estimate approach.⁸³ Finally, we will compare clinic-stratified intervention effects on the primary AD outcome and test their equality with a Breslow-Day test; the purpose is to identify 'large' differences where further investigation into potential protocol deviations or other factors may be warranted, and these results will be interpreted with caution.

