5.7. Analysis of Effect of Reported Emollient Use

Because the intervention uses an accessible, non-prescription topical emollient, either study arm might have users and non-users (compliant/non-compliant with study assignment). In the spirit of a *per-protocol analysis*, similar to the main analysis, we will classify participants by their reported emollient use (>weekly, on average, for the time up to diagnosis or end of follow-up) rather than assigned intervention arm. Under this coding, some participants assigned to the treatment arm might be non-users, and others assigned to the control arm may report regular emollient use; those individuals would be in different groups than under the main analysis, which uses assigned treatment arm.

Parent-reported frequency of emollient use (in days per week) will be summarized for the intervention and control arms for each quarterly follow-up time point from age 3 to 24 months (8 quarters). In this analysis, we will exclude observations after a diagnosis of AD, because emollient use is likely to reflect treatment rather than prevention. For example, if a parent reports a diagnosis of AD on the 9-month contact, that child's emollient use at 3 and 6 months will be included, but not 9 months or later. All of the definitions of AD diagnosis will be considered, i.e. GS-AD, PR-AD, CEQ-AD, etc. For missing responses, we will carry the last observation forward. Distributions over time will be graphed.

The relationship between frequency of emollient use and AD will be tested using a variable that is the average of each individual's frequency responses. We hypothesize that the intervention will increase the frequency of emollient use, and that more frequent emollient use will be associated with lower incidence of AD. If this is true, we expect that frequency will be associated with study arm (using a two-sample t-test or Wilcoxon rank-sum test, if skewed), that study arm will be associated with prevalence of AD (primary analysis), that higher frequency of emollient use will be associated with lower prevalence of AD (Equation 1 with emollient frequency substituted for study arm), and that including both treatment arm and emollient frequency in a model with AD as the outcome will change the estimate of treatment effect, which will be taken as evidence that frequency of emollient use is in the causal pathway.

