			Baths/week	Count (0-7+)	p%(x/n) n, mean, SD, Median, min, max
			Prior emollient use	Binary(Y/N)	p%(x/n)
			Prior emollient type	Categorical	p%(x/n)
			Prior emollient brand	Descriptive	p%(x/n)
Emollient Choices	Treatment Group	Baseline 24m or last refill	Prior emollient use per week	Count (0-7+)	p%(x/n) n, mean, SD, Median, min, max
			Gender	Binary(M/F)	p%(x/n)
			Ethnicity	Binary(Hispanic)	p%(x/n)
			Race	Categorical	p%(x/n)
			Education level	Categorical	p%(x/n)
			Emollient choice-baseline	Categorical	p%(x/n)
			Emollient choice-end of study	Categorical	p%(x/n)
			Switched from baseline	Binary(Y/N)	p%(x/n)

Table Title	Population	Time Point(s)	Endpoint	Endpoint Type	Summary Statistics by Treatment Assignment
Cumulative incidence of AD	ITT	24m	Primary outcome: Provider diagnosis of AD in patient chart	Binary(Y/N)	Relative risk(RR) for cumulative incidence
	ITT	12m,24m	Provider diagnosis of AD in patient chart at age 1 year and age 2 years	Binary(Y/N)	RR
	Complete case	12m,24m	Provider diagnosis of AD in patient chart (complete case)	Binary(Y/N)	RR
	ITT	12m,24m	Cumulative incidence of AD by parental report of provider diagnosis	Binary(Y/N)	RR
	ITT	12m,24m	Cumulative incidence of AD by parental report of Children's Eczema Questionnaire	Binary(Y/N)	RR
Age of onset of AD	ITT	All time points	Age of onset by chart review, parent report	Time to event	Kaplan-Meier
Skin Problems	ITT	12m,24m	Dry Skin	Binary(Y/N)	p%(x/n)
			Diagnosed eczema	Binary(Y/N)	p%(x/n)
			Red rash	Binary(Y/N)	p%(x/n)
			Itching	Binary(Y/N)	p%(x/n)
			Areas of rash	Categorical	p%(x/n)
Skin infections	ITT	12m,24m	Presence/absence at any time	Binary(Y/N)	p%(x/n)
			Type	Categorical	p%(x/n)
Rash treatment	AD population	12m,24m	Rash treatment Y/N	Binary(Y/N)	p%(x/n)
			Prescription treatment Y/N	Binary(Y/N)	p%(x/n)
			OTC treatment Y/N	Binary(Y/N)	p%(x/n)
			Specific type	Categorical	p%(x/n)
Skin care	ITT	12m,24m	Baths/week	Count(0-7)	p%(x/n) n, mean, SD, Median, min, max
			>2 baths/week	Binary(Y/N)	p%(x/n)
		12m,24m	>1 bath/week	Binary(Y/N)	p%(x/n)
		All time points before AD diagnosis, if applicable	Frequent emollient user: Report 3 or more days per week at majority of follow-up points	Binary(Y/N)	p%(x/n)
		Q3 months	Moisturizer use Y/N	Binary(Y/N)	p%(x/n)
			Emollient use days/week	Count(0-7)	n, mean, SD, Median, min, max
			Emollient type	Categorical	p%(x/n)
			Which emollients	Categorical	p%(x/n)

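### The SAP's per-protocol set is an as-treated comparison open to confounding by dry skin, and its user rule differs between sections

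*SAP*

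**What the plan says.** SAP section 3.6 states that the per-protocol population "will assign participants who report emollient use to the intervention arm (regardless of randomization"). Children with no reported use are placed with the controls. Section 5.7 repeats the regrouping and says that some children will sit in a different group from the one in the main analysis.

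The rule that makes a child a user is given in several ways:

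- SAP 3.6: any reported use against none.
- SAP 5.7: ">weekly, on average, for the time up to diagnosis or end of follow-up".
- Protocol 10.4.3: a model "substituting an indicator of regular reported emollient use (≥ 3 days per week) for intervention allocation", with no statement of how contacts are combined over time.
- SAP 5.12, Table 4, a descriptive row: "Frequent emollient user: Report 3 or more days per week at majority of follow-up points".

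Section 5.7 also has a model on average days per week of use, which needs no cut-off. It reuses Equation 1 with use in place of arm. Equation 1 (SAP 5.3) contains family history of atopy and a random effect for clinic, and rules out other baseline characteristics. Section 5.7 excludes emollient reports from the contact at which AD is reported onward. It also says that a change in the arm estimate, once frequency is added, will count as evidence that use lies on the causal pathway.

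On the control arm, Protocol 3.3.2 allows emollient as needed "if their baby develops dry skin", and the synopsis agrees. SAP 3.4 states the instruction without that exception. Protocol Table 1 lists xerosis among the features that support an AD diagnosis.

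**The concern.** A per-protocol set keeps children in their randomised arm and restricts to those who adhered. This one moves children between arms, so randomisation no longer protects the comparison. A control child is more likely to become a user if dry skin appears, and dry skin is plausibly an early sign of AD. Users would then carry more AD risk than non-users even if emollient did nothing.

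Two things are at stake. A reader may take a result labelled per-protocol as the effect of adherence. And the causal-pathway inference could be produced by confounding alone, because adding a confounded frequency variable can shift the arm coefficient. The differing user rules add a choice that can alter the answer.

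**Working it through.** **The plan's own figure.** The documents give no figure for this analysis. The design figure reproduces: with 24% against 16.8%, two-sided 0.05 and 80% power, n = [1.96·√(2 × 0.204 × 0.796) + 0.842·√(0.24 × 0.76 + 0.168 × 0.832)]² / 0.072² ≈ 491 per arm, as in SAP 2.3. With 20% loss, 491/0.8 = 614, within the planned 625. The 1,250 × 0.8 = 1,000 children with an outcome are used below.

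**Inputs.** From the documents: 24% AD and 1:1 allocation (SAP 2.3 and 2.2). Use in the intervention arm is set at 85%, after the pilot's 85.2% (Protocol 1.3), which was for use at least 5 times a week in a high-risk sample. Assumed: dry-skin prevalence d, AD risk ratio ρ for dry skin, and control use by dry-skin status.

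**Formula with no emollient effect.** Let uD and uN be use among dry-skin and other children, averaged over the arms, and U = d·uD + (1−d)·uN. The dry-skin share is q1 = d·uD/U among users and q0 = d·(1−uD)/(1−U) among non-users. Then

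RR = [1 + q1(ρ−1)] / [1 + q0(ρ−1)].

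This takes AD to be independent of arm and use given dry skin. If ρ = 1, RR = 1.00.

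**Middle case.** d = 30%, ρ = 2, control use 70% (dry skin) and 20% (other).

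- uD = (0.85 + 0.70)/2 = 0.775; uN = (0.85 + 0.20)/2 = 0.525; U = 0.2325 + 0.3675 = 0.600.
- q1 = 0.2325/0.600 = 0.388; q0 = 0.0675/0.400 = 0.169.
- AD risk without dry skin = 0.24/1.3 = 0.185. Users: 0.185 × 1.388 = 25.6%. Non-users: 0.185 × 1.169 = 21.6%. RR = 1.19.
- With 600 users and 400 non-users, SE(log RR) = √(0.744/153.7 + 0.784/86.3) = 0.118, so z = 0.172/0.118 = 1.45. The chance of a significant harm is P(Z > 1.96 − 1.45) = 31%, against a nominal 2.5%.

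**Ranges.**

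| Control use (dry / other) | d | ρ | Null RR |
|---|---|---|---|
| 70% / 20% | 20–40% | 1.5–2.5 | 1.08–1.28 |
| 80–90% / 70% | 30–40% | 1.5–2.0 | 1.03–1.13 |
| any of these | any | 1.0 | 1.00 |

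In the first row the chance of a significant harm is 10% to 53%. The second row reflects heavy background use: Protocol 1.5.1 cites over 70% daily moisturiser use. Its ends are:

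- Low (d = 30%, ρ = 1.5, use 80%/70%): q1 = 0.2475/0.79 = 0.313, q0 = 0.0525/0.21 = 0.250, RR = 1.157/1.125 = 1.03.
- High (d = 40%, ρ = 2, use 90%/70%): q1 = 0.350/0.815 = 0.429, q0 = 0.050/0.185 = 0.270, RR = 1.429/1.270 = 1.13.

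**Who the users are.** In the middle case intervention-arm children are 0.425/0.600 = 71% of users. In the heaviest-use case they are 0.425/0.815 = 52%.

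**Any-use rule with a pre-diagnosis window.** Suppose a 15% chance of sporadic use at each contact (assumed). A child never diagnosed has 8 contacts, so the chance of at least one report is 1 − 0.85⁸ = 73%. In SAP 5.7's own example of a diagnosis reported at 9 months, 2 contacts count, and the chance is 1 − 0.85² = 28%. Children without AD are thus pushed into the user group. A simulation of the quarterly contacts with no emollient effect and assumed onset times gave RR 0.50–0.59 for this rule, a false benefit. The same simulation gave 1.12–1.40 for more than weekly and 1.08–1.36 for at least 3 days a week. These show direction only, because they rest on the assumed onset times.

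**Alternatives on null data (85%; 70%/20%).** Comparison by randomised arm: RR 1.00, rejecting in 4–6%. Complier-average risk difference: 0.00. As-treated with adjustment for dry skin: RR 1.00, but only because dry skin was the sole confounder simulated.

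**The case against.** The plan has more protection than a quick reading suggests. Section 5.7 removes reports from diagnosis onward, because later use probably reflects treatment. Family history and clinic are already in the model. Section 5.7 describes the analysis as only in the spirit of per-protocol and says openly that groups differ from the main analysis. The frequency model has no cut-off, and the Table 4 row is descriptive. These points stand and narrow the concern. They do not remove it: use prompted by dry skin before diagnosis is untouched, the frequency model shares that confounding, and the two SAP sections still define a user differently.

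Stronger readings are tempting but unsupported:

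- *The analysis compares dry-skin users with everyone else.* More than half of users are intervention-arm children in every scenario worked. Dry-skin children are over-represented among users, not the whole group.
- *It will show harm.* The bias vanishes if dry skin carries no AD risk, shrinks with heavy background use, and can turn towards benefit under the any-use rule.
- *There are four competing exposure definitions.* Three rules bear on the analysis. The Table 4 row shares the 3-day threshold and adds a majority-of-contacts version.
- *The choice between more than weekly and at least 3 days a week drives the result.* Their simulated ranges overlap almost entirely.

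**Conclusion.** The concern holds for secondary analyses. The population is as-treated, its label is wrong, and its model omits a likely confounder that is recorded at baseline. With no emollient effect, the expected RR for users against non-users is about 1.03 to 1.3 in the scenarios worked. Those rest on assumed dry-skin prevalence (20–40%), AD risk ratio for dry skin (1.5–2.5) and use rates. The documents give neither dry-skin figure, nor use by dry-skin status in this trial, and milder assumptions bring the RR closer to 1.00. The binary user rule conflicts between SAP 3.6, SAP 5.7 and Protocol 10.4.3, and the direction of bias can depend on which is used. A reader might infer that the trial's main conclusion is at risk. It is not: the primary test compares children as randomised (SAP 5.3), and neither that test nor the sample size is affected.

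**What to change.** 1. Rename the population and the section 5.7 analysis as-treated (observational).
2. Use one pre-diagnosis user rule, based on average frequency and not on any use, in Protocol 10.4.3, SAP 3.6, SAP 5.7 and Table 4. Say how a child diagnosed by the 3-month contact, with no usable report, is classified.
3. Add baseline dry skin and prior emollient use to this model. Both are already listed among the baseline variables in Table 4. State that confounding by dry skin that develops later remains, since a measurement at 0 to 2 months cannot capture it.
4. Remove the statement that a changed arm coefficient is evidence of a causal pathway.
5. As a supplement, report a complier-average estimate with randomised arm as the instrument.

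Items 1 to 4 cost SAP and protocol wording and two covariates already collected. Item 5 is one extra model. Its interval will be wider, and it assumes that assignment acts only through the chosen definition of use. That is doubtful when background use is mostly watery lotions (Protocol 1.5.1) and intervention families receive lipid-rich products, so it should not replace the ITT result.

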4.1. Screening Data

We will prepare a flow chart of the numbers of interested individuals who are not eligible or choose not to participate based on the criteria detailed in the following sections and listed below in order of appearance on screening tools:

Language preference (English/Spanish)

PBRN (based on clinic)

Contact information provided (Email / Text-capable phone number / *Neither email nor text-capable phone*)

Are you a parent or guardian with custody of a baby that is less than 2 months old (about 9 weeks)?

Are you 18 years or older?

Do you have convenient access to the internet?

Did your baby weigh MORE than 2.2 pounds (2 pounds, 3 ounces or 1,000 grams) at birth?

Was your baby born more than 3 months early?

Has YOUR BABY been diagnosed with eczema or atopic dermatitis by a medical provider?

Has your baby been diagnosed with an immunodeficiency genetic syndrome, such as Wiskott-Aldrich Syndrome or Severe Combined Immunodeficiency Syndrome?

Do you have another child enrolled in the CASCADE study?

Declines to participate

We will capture all criteria that potential participants fail to meet. For the first three items (PBRN, language, and preferred contact modality) we will compare participants and non-participants. The remaining items relate to exclusion criteria and by definition will not describe participants. These data will be discussed within the context of different recruitment methods at each site within PBRNs.

